5.9 Definition of an inadequate response

If patients show evidence of persistent loss of disease control (on clinical or haematological or biochemical or CH50 parameter), the Investigator may increase the dose or the dose frequency in line with the **table in section 5.10** if they are not already on the maximum permitted dose. This should only be done in consultation with the Sponsor's Medical Director and after other possible causes such as poor compliance have been eliminated. The subject may require additional investigations (including blood tests) to evaluate loss of disease control and dose adjustment.

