Female patients must agree not to breastfeed whilst on the trial and for at least 90 days after the last day of IMP administration.

5. Trial Design and Procedures

5.1. Trial Design:

The trial is an open-label, non-comparative study in approximately 50 patients, 18 years and above with either PNH or aHUS who have participated in another rVA576 (Coversin) and who wish to remain on the study.

5.2. Dose Changes:

If the Investigator considers that a change in dose or dose frequency is necessary, it is suggested that the schedule shown in **Table 7** is followed. Please note that Ablating Doses may only be needed if the change is to a higher dose or dose frequency. A change to an increased dose is mandated by an inadequate response (see definition below) but may also occur at the discretion of the Investigator in consultation with the Sponsor.

Table 7: Dose Decision Table: Suggested schedule for changing dose/dose interval in case of inadequate response

PNH patients

Ablating Doses (if required)			
Dose		Interval	
60mg		Single dose	
30mg		1 x 12 hourly dose	
Inadequate Response			
Existing		Switch to	
Dose	Interval	Dose	Interval
15mg	12 hourly	22.5mg	12 hourly
22.5mg	12 hourly	45mg	24 hourly
30mg	24 hourly	45mg	24 hourly
45mg	24 hourly	22.5mg	12 hourly

aHUS patients

Note: aHUS pts from the parent study will rollover to AK581 with the dosing regimen (taken) on the last dosing day of the parent study

Ablating Doses (if required)			
Dose		Interval	
60mg		Single dose	
30mg		1 x 12 hourly dose	
Inadequate Response			
Existing		Switch to	
Dose	Interval	Dose	Interval
30mg	12 hourly	After assessment decision will be made in collaboration with the Sponsor and PI.	
45mg	24 hourly	30mg	12 hourly

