5.5 Measurements conducted on blood draws

5.5.1 CH50 assay

It appears that in PNH and aHUS, close to 100% inhibition of CH50 activity is necessary for clinical control of the disease. Serum CH50 assay is currently the most sensitive and quickest means of detecting inadequate control during anti-complement therapy as other indicators, such as LDH lag 24 - 48 hours behind the change in CH50. In practice, the Quidel ELISA assay, which is used to measure complement activity in units of CH50 U Eq/mL has a lower limit of quantification (LLOQ) of 10 CH50 U Eq/mL with individual normal baseline values ranging from 58-156 CH50 U Eq/mL. Thus the assay is insensitive to differences in CH50 when there is <10 CH50 U Eq/mL residual complement activity. Therefore, for practical purposes, the Central Laboratory (which will conduct all CH50 assays during the trial) considers values less than 10 CH50 U Eq/mL as completely inhibited. In previous trials (AK577, AK578 and AK579) with rVA576 (Coversin) the LLOQ of the CH50 was 8 CH50 EU/mL. The LLOQ has increased because the assay is now being performed using an automated system for the ELISA.

CH50 samples will be collected as per Schedule of Events.

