6.2 Withdrawal criteria

In accordance with applicable regulations, a patient has the right to withdraw from the study at any time and for any reason, without prejudice to their future medical care by the physician or at the Institution. Should a patient withdraw from the study, then the patient will not undergo any further study-specific procedures or receive any treatment mandated by the protocol.

If a subject fails to attend scheduled trial assessments, the Investigator must determine the reasons and the circumstances as completely and accurately as possible.

In the event of the premature withdrawal of a patient from the trial, the end of trial visit should be carried out as completely as possible. Minimally, a safety assessment should be performed.

In the case of withdrawal due to the occurrence of unacceptable toxicity, the patient will be requested to remain under the supervision of the Investigator until the toxicity has resolved or is no longer considered to be clinically significant by the Investigator.

If an Adverse Event classified as severe results in patient withdrawal from the study, the subject will be followed until the AE (or SAE) resolves or stabilises, and any interventions required to resolve or stabilise the event will be recorded in the eCRF.

All withdrawals must be documented in the eCRF. A patient may be withdrawn in any of the following circumstances.

- Withdrawal of consent (mandatory withdrawal)
- Intake of non-permitted concomitant medication (may be discussed with the Sponsor and dependent on the nature of the medication)
- Patient is non-compliant with more than three consecutive missed doses and two missed clinic visits, in the opinion of the Investigator (discretionary withdrawal)
- If discontinuation is considered necessary by the Investigator and/or Sponsor (mandatory withdrawal)
- Request of Regulatory Agency (mandatory withdrawal)
- Patient develops an illness that would compromise his participation in the study (may be discussed with sponsor)
- Patient is not achieving complete inhibition at the maximum assigned dose (inadequate response to rVA576 (Coversin) treatment)
- Pregnancy, unless the patient wishes to consent to a termination.

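### The protocol's rules for acting on an inadequate response contradict each other, and the PNH switching schedule has no final step

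*Protocol*

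**What the plan says.** Five places in the protocol bear on this.

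- **Section 5.2 (Dose Changes).** "A change to an increased dose is mandated by an inadequate response (see definition below"). For the change itself, "it is suggested that the schedule shown in" Table 7 be followed. The synopsis prints the same PNH and aHUS schedules.
- **Section 5.9 (Definition of an inadequate response).** The trigger is that patients "show evidence of persistent loss of disease control (on clinical or haematological or biochemical or CH50 parameter"). The action is worded as a choice ("the Investigator may increase the dose or the dose frequency in line with the"). The schedule cited for it is the "table in section 5.10". The step is limited to patients below a ceiling ("if they are not already on the maximum permitted dose"). The Sponsor's Medical Director must be consulted and other causes, such as poor compliance, excluded first.
- **Section 5.10 (Missed doses).** Its table gives catch-up dosing by how late a dose is. It is not an escalation schedule.
- **Section 6.2 (Withdrawal criteria).** One listed circumstance is: "Patient is not achieving complete inhibition at the maximum assigned dose (inadequate response to rVA576 (Coversin) treatment"). On what complete inhibition means, section 5.5.1 says the Central Laboratory "considers values less than 10 CH50 U Eq/mL as completely inhibited".
- **Synopsis, Treatment Regimen.** It assumes that dose or dose frequency would be reduced only where complement control had been adequate beforehand.

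**The concern.** These passages tell a site what to do when a patient loses disease control. Read together, they leave four things unclear: whether an increase is required, which table to use, where the PNH schedule stops, and what the term means when it becomes a reason for withdrawal. Two sites could treat similar PNH patients differently and both be following the protocol.

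The first stake is patient safety. A site that follows section 5.9 literally opens the wrong table, and the schedule it should have reached does not end for PNH.

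The second is interpretation. SAP section 1 says no aHUS patients will enter, so the PNH schedule is the one that governs the analysed population. Protocol section 9.8 and SAP section 4.2.2 analyse efficacy at each time point in the patients who reach it, and protocol section 9.1 by default leaves missing data out of percentage denominators. Who is kept on treatment and who is withdrawn therefore affects who contributes to later summaries. The SAP's table list (section 7.1) includes no summary of dose changes or inadequate-response episodes that would show such differences.

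**Working it through.** The plan states no figure to reproduce. The check is a comparison of passages plus daily totals from Table 7, using daily total = dose × 24 / interval in hours.

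**Verb.** Section 5.2 mandates an increased dose. Section 5.9 says the Investigator may increase dose or frequency. These differ both in obligation and in what counts as an increase.

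**Table.** Section 5.9 cites section 5.10 (missed doses). The table titled for inadequate response is Table 7 in section 5.2.

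**PNH rows of Table 7 (same in the synopsis).**

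| Existing | Daily total | Switch to | Daily total | Change | Doses per day |
|---|---|---|---|---|---|
| 15 mg 12-hourly | 15 × 2 = 30 mg | 22.5 mg 12-hourly | 22.5 × 2 = 45 mg | +15 mg | 2 → 2 |
| 22.5 mg 12-hourly | 22.5 × 2 = 45 mg | 45 mg 24-hourly | 45 × 1 = 45 mg | 0 | 2 → 1 |
| 30 mg 24-hourly | 30 × 1 = 30 mg | 45 mg 24-hourly | 45 × 1 = 45 mg | +15 mg | 1 → 1 |
| 45 mg 24-hourly | 45 × 1 = 45 mg | 22.5 mg 12-hourly | 22.5 × 2 = 45 mg | 0 | 1 → 2 |

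Following the rows from each start:

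- 15 mg 12-hourly → 22.5 mg 12-hourly → 45 mg 24-hourly → 22.5 mg 12-hourly, and so on.
- 30 mg 24-hourly → 45 mg 24-hourly → 22.5 mg 12-hourly → 45 mg 24-hourly, and so on.

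All four starts end in the same pair of regimens, and no PNH row is terminal. A patient starting at 30 mg/day returns to a regimen already tried only after three inadequate responses; one starting at 45 mg/day, after two.

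The aHUS schedule does end: 45 mg 24-hourly (45 mg/day) → 30 mg 12-hourly (30 × 2 = 60 mg/day) → a decision by Sponsor and PI.

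**Conflict with the synopsis.** The row from 22.5 mg 12-hourly to 45 mg 24-hourly halves dose frequency in response to an inadequate response. The synopsis contemplates a lower frequency only when prior control was adequate.

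**Term.** A patient with CH50 below 10 U Eq/mL but persistently rising LDH and haemolysis fits section 5.9 and not the item in section 6.2. A patient with persistently incomplete inhibition below the maximum dose also fits 5.9 and not 6.2.

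**Maximum.** Sections 5.9 and 6.2 both depend on a maximum dose, and the readable text gives no value. Two cases cover the possibilities:

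- If the maximum is one of the four PNH regimens in Table 7, Table 7 still names a switch away from it.
- If it is some other regimen, the PNH schedule never reaches it. The PNH missed-dose table does list 30 mg 12-hourly (60 mg/day), which has no row in PNH Table 7.

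**The case against.** Much can be said for the protocol. Table 7 is only a suggestion, changes under section 5.9 need Sponsor consultation, and the synopsis makes monitoring of complement inhibition mandatory during a change, including LDH, CH50 and clinical status. Unsupervised alternation is not what the text describes. Daily total is not a yardstick the protocol states, and moving from 45 mg 24-hourly to 22.5 mg 12-hourly does raise frequency, which section 5.9 allows. Section 6.2 can be read as a deliberately narrower withdrawal trigger rather than a second definition, and section 5.5.1 itself ties near-complete CH50 inhibition to clinical control. The maximum dose may sit in redacted text. All of this stands, and it limits the point.

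It does not remove the contradictions. Consultation does not settle whether an increase is required or correct the table reference. The frequency argument covers one of the two paired rows; the other lowers frequency. A narrower trigger in 6.2 still carries the same label as 5.9.

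A reader might infer that this is the study's only criterion for loss of response, or that a failing PNH patient has no way out. The documents do not support either. Section 5.4.3 allows withdrawal for lack of efficacy, section 6.2 separately covers discontinuation judged necessary by Investigator or Sponsor, and LDH categories, haemolytic events and transfusions are assessed independently of the dosing rule. Nor could the patient with CH50 below 10 be withdrawn elsewhere on CH50 alone, because the item in 6.2 requires incomplete inhibition.

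**Conclusion.** The point holds as an internal inconsistency in how an inadequate response is handled, chiefly for PNH. Its size on the page is:

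- one conflict of obligation (5.2 against 5.9);
- one wrong table reference (5.9);
- two of four PNH rows with no change in daily total that lead back to each other, and none of the four a final step;
- one term used with two scopes (5.9 and 6.2), with no readable maximum.

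It is tempting to go further and say that the LDH and haemolysis results depend on which passage a site followed. That is not shown. Inadequate response is not an endpoint in either document, all analyses are descriptive, and the documents do not say how many patients would be affected. The route to the results is indirect, through inconsistent dose changes and withdrawals.

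The remark on the missing maximum assumes that no redacted passage supplies it. If one does, that remark reduces to a missing cross-reference; the verb, table, paired rows and scope of the term still need reconciling. The reason to act is consistent care of patients losing disease control, at little cost.

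**What to change.** The sponsor should reconcile the synopsis and protocol sections 5.2 (with Table 7), 5.9, 5.10 and 6.2:

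1. Correct the table reference in section 5.9.
2. Use one verb for the response to an inadequate response in sections 5.2 and 5.9.
3. Give the term one meaning, or use a different label in section 6.2 if a narrower withdrawal trigger is intended.
4. State how the PNH schedule ends, and resolve the row that lowers frequency against the synopsis assumption.
5. State which regimen counts as the maximum, and reconcile the regimens listed for PNH in section 5.10 with those in Table 7.

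The clinical team must decide the doses and rules; none is proposed here.

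Optionally, record in the eCRF which criterion was met at each dose change or lack-of-efficacy withdrawal. Withdrawals are already documented and their primary reasons summarised (protocol section 6.2, SAP section 4.6), so this adds only the criterion.

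The cost is a protocol clarification or amendment to a few paragraphs and one schedule printed in two places, plus one eCRF field if the option is taken. No planned analysis changes.

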5.10 Missed doses

For PNH patients:

For a missed dose of more than >24 hours, the sample for PD (CH50) analysis should be taken if possible just prior to the next morning dose of rVA576 (Coversin). As the CH50 results will not be available for some days the Investigator should be guided by the history, clinical signs or platelet count and LDH. In some cases, the PI may feel that an ablating dose is not required and the patient should resume their usual dosing schedule as soon as possible. In PNH, clinical signs of intravascular haemolysis following resumption of dosing mandates re-initiation of the AD schedule. The CRO and the Sponsor should be informed as soon as possible.

Dose	Interval	Missed Dose <4hr	Missed Dose <24hrs	Missed dose by day(s)>24hrs
15mg	12 hourly	Dose to be taken as soon as patient realizes	Take 15mg dose immediately and 15mg dose at usual time	Take ablating dose 60mg/30mg. then take dose as per usual routine
22.5mg	12 hourly		Take 22.5mg dose immediately and 22.5 mg dose at usual time	
30mg	12 hourly		Take 30mg dose immediately and 30mg dose at usual time	
30mg	24 hourly		Take 45mg dose immediately and 45mg dose at usual time	
45mg	24 hourly		Take 45mg dose immediately and 45mg dose at usual time	

For aHUS patients:

In the event of one missed dose (defined as a dose not taken within a one-hour time window either side of the specified time) the following procedure should be adopted by the patient:

- Take the appropriate dose as per the day of the protocol as soon as possible and then resume the usual dosing schedule at the specified times

In the event of more than one missed dose the CRO and the Investigator's clinic should be informed as soon as possible and the following procedure should be adopted:

- Take 60 mg Coversin followed by 30 mg 12 hours later and then resume the usual dosing schedule (i.e. between 07:00 and 11:00 hrs daily) at the first time point after the ablation doses.

The Investigator's clinical staff should arrange for a Central laboratory blood draw for PK/PD to be taken 3 days \pm 1 day after first becoming aware of the missed doses in this situation.

The sample for PD (CH50) analysis should be taken just prior to dosing with rVA576 (Coversin).

As the CH50 results are unlikely to be available for some days the Investigator should be guided by the history, clinical signs or platelet count and LDH as to whether it is necessary to administer additional Ablating Doses.

If 3 or more consecutive doses have been missed the patient's ability or willingness to comply with the protocol should be discussed and consideration should be given as to whether that subject should continue in the study.

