At the last scheduled visit, the Investigator shall instruct each patient to report any subsequent event(s) that the patient, or her personal physician, believes might reasonably be related to participation in this Study. The Investigator should notify the Sponsor (or designee) of any death or SAE occurring at any time after a patient has discontinued or terminated study participation that may reasonably be related to this Study.

7.2.2 *Pre-existing Conditions*

For purposes of this Study a pre-existing condition means a diagnosis, clinically significant finding, symptom, or laboratory abnormality present at baseline (Visit 1). Subsequently, during the course of the Study it shall be recorded as an AE/SAE if the frequency, intensity, or the character of the condition worsens during the study period.

7.2.3 *Overdose*

All overdoses with or without associated symptoms, should be reported as AEs on the appropriate eCRF page. An overdose is defined as a dose of 90mg or above in a 24 hour period. If sequelae meeting the criteria for a SAE have occurred in association with the overdose, the case must be reported immediately, within 24 hours. Action to be taken, if any, in event of an overdose should be discussed with the Sponsor's medical representative at the earliest opportunity. However, in animal toxicology, no adverse events have been observed following single intravenous doses of approximately 50 times the human therapeutic dose, so no specific toxicity is anticipated. There are no known antidotes to rVA576 (Coversin) and observation and supportive treatment are the only recommended measures. An assessment of whether the overdose was accidental or intentional should be recorded. If the overdose was a suicide attempt, this fact should be clearly stated. The AEs and SAEs that occur as a result of an overdose should be recorded on the eCRF.

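### One PNH missed-dose row gives 45 mg + 45 mg to patients on 30 mg once daily, and the 90 mg overdose rule makes the protocol's own ablating regimen a reportable adverse event

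*Protocol*

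**What the plan says.** **Missed doses.** The PNH table in Protocol 5.10 gives an instruction by current regimen and by how late the dose is. In the column for less than 24 hours, the 30 mg 12-hourly row reads "Take 30mg dose immediately and 30mg dose at usual time". The 15 mg and 22.5 mg 12-hourly rows and the 45 mg 24-hourly row likewise repeat the patient's own dose. The 30 mg 24-hourly row reads "Take 45mg dose immediately and 45mg dose at usual time", the same text as the 45 mg row beneath it. For more than 24 hours the instruction is "Take ablating dose 60mg/30mg. then take dose as per usual routine". The text above the table lets the investigator omit the ablating dose in some cases.

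**Other ablating doses.** Protocol 6.5 requires the same 60 mg then 30 mg after any interruption longer than 24 hours. The Synopsis and 5.2 allow it when dose or frequency is increased.

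**Overdose.** Protocol 7.2.3 states: "An overdose is defined as a dose of 90mg or above in a 24 hour period". Every overdose is to be reported as an adverse event, whether or not there are symptoms. Doses that the protocol directs are not exempted.

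**Where adverse events go.** They are part of the primary endpoint (Protocol 3.2.1, SAP 2.4.1). SAP 3.4.3 treats all of those recorded in this study as treatment-emergent, and SAP 4.12.1 tabulates both patients and events.

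**Dose increases.** Protocol 5.9 says that "the Investigator may increase the dose or the dose frequency in line with the" table in section 5.10. The escalation schedule is Table 7 in section 5.2, titled "Dose Decision Table: Suggested schedule for changing dose/dose interval in case of inadequate response".

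**The concern.** Patients prepare and inject the drug themselves, so a table cell is in effect the prescription. A patient on 30 mg once daily who follows the printed row takes one and a half times the amount that the rest of the table would give, with no stated reason.

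The overdose rule raises a different problem. In a long-term safety study, an adverse event should record something untoward. Here a patient who follows the ablating instruction exactly, and feels nothing, meets the definition of a reportable event. Some sites may apply the rule literally and others may not, and the safety tables would then partly reflect reporting habit.

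The reference in 5.9 is clerical: an investigator sent to 5.10 for a dose increase finds only missed-dose instructions.

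**Working it through.** No sample size, power or error rate is involved. The check is a comparison of rows and a sum of doses against the one stated figure, 90 mg in a 24 hour period (Protocol 7.2.3).

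**Step 1: the make-up pair** (immediate dose + dose at the usual time, Protocol 5.10, late by less than 24 h).

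| Regimen | Printed pair | Own-dose pair | Ratio |
|---|---|---|---|
| 15 mg 12-hourly | 15 + 15 = 30 mg | 30 mg | 1.0 |
| 22.5 mg 12-hourly | 22.5 + 22.5 = 45 mg | 45 mg | 1.0 |
| 30 mg 12-hourly | 30 + 30 = 60 mg | 60 mg | 1.0 |
| 30 mg 24-hourly | 45 + 45 = 90 mg | 30 + 30 = 60 mg | 90/60 = 1.5 |
| 45 mg 24-hourly | 45 + 45 = 90 mg | 90 mg | 1.0 |

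One row of five departs from the pattern, by 90 − 60 = 30 mg.

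**Step 2: the ablating regimen against the threshold.** 60 + 30 = 90 mg, with the two doses 12 h apart. This reaches 90 mg inside any 24 h span that holds both doses. If 7.2.3 were applied by calendar date, it would still be met whenever the first dose is taken before noon, because both doses then fall on one date.

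**Step 3: make-up doses against the threshold, on a rolling 24 h window.** The rolling window is an assumption, since 7.2.3 does not say how the 24 hours are counted. Let a dose due at 0 h be taken t hours late, before the next scheduled dose.

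- 24-hourly rows: doses at t and 24 h, span 24 − t (t = 4 gives 20 h). The 45 mg row totals 90 mg. The 30 mg row totals 90 mg as printed and 60 mg if corrected.
- 12-hourly rows: doses at t, 12 and 24 h, span 24 − t (t = 5 gives 19 h). Totals are 3 × 15 = 45 mg, 3 × 22.5 = 67.5 mg and 3 × 30 = 90 mg. The third dose is the next regular one and is not part of the row's own instruction.

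**Step 4: does correcting the row remove the overdose conflict?** No. The corrected row falls to 60 mg, below the threshold. The ablating regimen stays at 90 mg on the plain reading. On the rolling reading, so do the 45 mg 24-hourly make-up and the 30 mg 12-hourly make-up with the next two scheduled doses. The two defects need separate fixes.

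**The case against.** The strongest reply on the row is that 45 mg may be deliberate. Table 7 moves a patient on 30 mg 24-hourly to 45 mg 24-hourly, so a boosted make-up dose has some logic, and much of the background is redacted. This stands: the row is a probable error, not a proven one, and the sponsor must be able to confirm it.

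A reader might infer that the row bypasses 5.9, which asks for Sponsor consultation and allows an increase only "after other possible causes such as poor compliance have been eliminated". The documents do not support that. Section 5.9 governs increases for persistent loss of disease control, whereas this is a two-dose make-up instruction. Nor does the row change the maintenance dose; it only leaves the return to 30 mg unstated. Harm to patients is not shown either: the printed total equals that of the ablating regimen, and 7.2.3 expects no specific toxicity.

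On overdose, the make-up totals depend on the rolling window. Under that reading a 45 mg 24-hourly dose taken one hour late already counts (45 + 45 = 90 mg in 23 h), which suggests that the authors may have meant a dosing day. A dose due at 8 am, taken at 8 pm and followed by the next at 8 am gives 45 mg on each date. This limits the make-up part of the point. It does not rescue the ablating regimen, which places 90 mg within 12 hours. Reading the threshold as a single injection would remove the conflict, but would leave the reference to a 24 hour period without purpose.

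The wrong reference in 5.9 is unlikely to cause a wrong increase. Section 5.2 and the Synopsis carry the correct schedule, and the Sponsor's Medical Director must be consulted.

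**Conclusion.** The point holds for dosing and adverse-event reporting instructions as they are printed.

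1. The 30 mg 24-hourly row gives 90 mg where the table's pattern gives 60 mg. It is probably copied from the row below; intent cannot be excluded on the visible text.
2. The ablating regimen totals 90 mg in 12 hours and so meets the overdose definition. Correct, symptom-free dosing becomes a treatment-emergent adverse event in the primary safety endpoint. That the 45 mg 24-hourly make-up, and the 30 mg 12-hourly make-up with the next two scheduled doses, also reach 90 mg holds only on a rolling 24 hour count.
3. The reference in 5.9 is clerical.

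A reader might infer that the primary safety results would be materially distorted. The documents do not support this. They give neither the number of patients on 30 mg 24-hourly nor the expected number of ablating or make-up episodes, so no percentage can be attached. Treatment lasts up to 4 years and nearly all adverse events are reported, so most affected patients would probably have another event anyway. The any-AE proportion should move little, and overdose entries could be identified in the listings. The aHUS rescue doses should not be added to the argument, because the SAP states that no aHUS patients will enter.

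**What to change.** One protocol amendment covers all three parts.

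1. **5.10, PNH table.** Change the 30 mg 24-hourly row to 30 mg immediately and 30 mg at the usual time. If the sponsor confirms that 45 mg is intended, keep it, give the reason, and state that 30 mg then resumes.
2. **7.2.3.** Exclude from the overdose definition any total reached only through the regular schedule and doses given as directed in 5.2, 5.10 and 6.5. Record those doses in the dosing data with a protocol-directed flag, and continue to report any associated sign or symptom as an adverse event. The flag is needed because a bare exemption would lose sight of symptom-free exposures of 90 mg or more in a safety study.
3. **5.9.** Cite Table 7 in section 5.2 in place of the table in section 5.10.

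The cost is the amendment, a letter to sites, a flag in the dosing data, and a data-review check for overdose events already recorded for protocol-directed doses. No new patients, assessments or analyses are needed.
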